## **6. ADVERSE EVENTS**

### **6.1 Expected Toxicities**

Slight transient discomfort at the puncture site as the needle is inserted is expected. Minimal bleeding that can be controlled by temporary pressure and bruising at the needle site are potential sequelae.

Toxicity Management is per phlebotomy lab standards

### **6.2 Adverse Event Reporting**

No particular adverse events are expected from participation in this protocol. The participants will be exposed to the minor increased risk accrued from repeated peripheral blood sampling.

## **7. MEASUREMENT OF EFFECT**

Not applicable in this protocol, as response to therapy will be judged per protocol specific to the therapy being received, which will vary from patient to patient.

## **8. DATA REPORTING / REGULATORY REQUIREMENTS**

Adverse event lists, guidelines, and instructions for AE reporting can be found in Section 6.0 (Adverse Events: List and Reporting Requirements).

### **8.1 Data Reporting**

#### **8.1.1 Method**

The QACT will collect, manage, and perform quality checks on the data for this study.

#### **8.1.2 Responsibility for Data Submission**

Investigative sites within DF/HCC or DF/PCC are responsible for submitting data and/or data forms to the QACT according to the schedule set by the QACT.

### **8.2 Data Safety Monitoring**

Involvement in this study as a participating investigator implies acceptance of potential audits or inspections, including source data verification, by representatives designated by the DF/HCC Overall Principal Investigator (or Protocol Chair) or DF/HCC. The purpose of these audits or inspections is to examine study-related activities and documents to determine whether these activities were conducted and data were recorded, analyzed, and accurately reported in accordance with the protocol, institutional policy, Good Clinical Practice (GCP), and any applicable regulatory requirements.

All data will be monitored for timeliness of submission, completeness, and adherence to protocol requirements. Monitoring will begin at the time of participant registration and will continue during protocol performance and completion.

### **8.3 Protocol Review and Amendments**

This protocol, the proposed informed consent and all forms of participant information related to the study (e.g., advertisements used to recruit participants) and any other necessary documents must be submitted, reviewed and approved by a properly constituted IRB governing each study location.

Any changes made to the protocol must be submitted as amendments and must be approved by the IRB prior to implementation. Any changes in study conduct must be reported to the IRB. The DF/HCC Overall Principal Investigator (or Protocol Chair) will disseminate

protocol amendment information to all participating investigators.

All decisions of the IRB concerning the conduct of the study must be made in writing.

#### **8.4 Ethics and Good Clinical Practice (GCP)**

This study is to be conducted according to the following considerations, which represent good and sound research practice:

- E6 Good Clinical Practice: Consolidated Guidance  
[www.fda.gov/downloads/RegulatoryInformation/Guidances/UCM129515.pdf](http://www.fda.gov/downloads/RegulatoryInformation/Guidances/UCM129515.pdf)
- US Code of Federal Regulations (CFR) governing clinical study conduct and ethical principles that have their origin in the Declaration of Helsinki
  - Title 21 Part 11 – Electronic Records; Electronic Signatures  
[www.access.gpo.gov/nara/cfr/waisidx\\_02/21cfr11\\_02.html](http://www.access.gpo.gov/nara/cfr/waisidx_02/21cfr11_02.html)
  - Title 21 Part 50 – Protection of Human Subjects  
[www.access.gpo.gov/nara/cfr/waisidx\\_02/21cfr50\\_02.html](http://www.access.gpo.gov/nara/cfr/waisidx_02/21cfr50_02.html)
  - Title 21 Part 54 – Financial Disclosure by Clinical Investigators  
[www.access.gpo.gov/nara/cfr/waisidx\\_02/21cfr54\\_02.html](http://www.access.gpo.gov/nara/cfr/waisidx_02/21cfr54_02.html)
  - Title 21 Part 56 – Institutional Review Boards  
[www.access.gpo.gov/nara/cfr/waisidx\\_02/21cfr56\\_02.html](http://www.access.gpo.gov/nara/cfr/waisidx_02/21cfr56_02.html)
  - Title 21 Part 312 – Investigational New Drug Application  
[www.access.gpo.gov/nara/cfr/waisidx\\_02/21cfr312\\_02.html](http://www.access.gpo.gov/nara/cfr/waisidx_02/21cfr312_02.html)
- State Laws
- DF/HCC research policies and procedures  
<http://www.dfhcc.harvard.edu/clinical-research-support/clinical-research-unit-cru/policies-and-procedures/>

It is understood that deviations from the protocol should be avoided, except when necessary to eliminate an immediate hazard to a research participant. In such case, the deviation must be reported to the IRB according to the local reporting policy.

#### **8.5 Study Documentation**

The investigator must prepare and maintain adequate and accurate case histories designed to record all observations and other data pertinent to the study for each research participant. This information enables the study to be fully documented and the study data to be subsequently verified.

Original source documents supporting entries in the case report forms include but are not limited to hospital records, clinical charts, laboratory and pharmacy records, recorded data from automated instruments, microfiches, photographic negatives, microfilm or magnetic media, and/or x-rays.

#### **8.6 Records Retention**

All study-related documents must be retained for the maximum period required by applicable federal regulations and guidelines or institutional policies.

## 9. STATISTICAL CONSIDERATIONS

### 9.1 Study Design/Endpoints

**Primary Objective: To determine the sensitivity and specificity of the peripheral blood BRAFV600 mutation detection.**

Two cohorts of melanoma patients will be assessed using the blood-based assay: patients with advanced disease (non-resectable Stage III or Stage IV), and patients with Stage II and resectable Stage III disease. Assessments of diagnostic accuracy, such as sensitivity, specificity, and positive predictive value (PPV) of the blood-based assay, will be compared separately for the two cohorts, and will use paired binary data. Sample size estimates are based on the binomial distribution and joint 90% confidence regions for sensitivity and specificity to adjust for the two comparisons being performed. Positive and negative expression will be determined using optimized cut points for the assay that have already been established.

We are seeking evidence that the assay has the ability to detect both the presence of BRAF mutation in melanoma (sensitivity) and accurately indicate when a BRAF mutation is not present (specificity) in order to provide BRAF-directed therapy when indicated. We propose a sample of 110 patients with advanced melanoma to test the performance of the assay, and would require sensitivity of at least 0.80 and specificity of at least 0.90. We set our target sensitivity to be 0.90 and specificity to 0.95. With a sample size of 110 patients (approximately 55 with BRAF mutation and 55 without) and the assumed target sensitivity, the lower bound of the joint 90% confidence region will be greater than 0.82; the lower bound of the 90% joint confidence region for the specificity will be approximately 0.90.

We will also estimate the PPV of the assay to evaluate the practical utility of the test. Based on a sample size of 110 patients, Table 1 summarizes the estimated PPV and corresponding 90% confidence intervals over a range of prevalence rates of BRAF mutation, using the minimum and target levels of sensitivity and specificity. With a sample of 110 patients, the lower bound of the 90% confidence interval for PPV will be no less than 0.74.

Table 1 – Estimates of PPV and 90% Confidence Intervals

Prevalence Rate	Sensitivity	Specificity	PPV	90% Confidence Interval for PPV
0.4	0.80	0.90	0.84	(0.74 to 0.91)
	0.90	0.95	0.92	(0.83 to 0.97)
0.5	0.80	0.90	0.89	(0.80 to 0.94)


Obuchowski NA. Sample size calculations in studies of test accuracy. *Stat Methods in Medical Res* 1998; 7: 371-392.

	0.90	0.95	0.95	(0.87 to 0.98)
0.6	0.80	0.90	0.92	(0.85 to 0.96)
	0.90	0.95	0.96	(0.90 to 0.99)

The cohort of patients with Stage II and resectable Stage III melanoma is an exploratory cohort. We cannot predict the sensitivity and specificity of the assay in patients with Stage II or resected Stage III disease. In addition, only patients in this cohort with T4 disease or macrometastatic lymph nodes will have adequate tissue for assessment. However, we believe it is important to include this cohort since the ability to detect BRAF in this patient population may provide a basis for proposing further studies correlating BRAF detection with disease recurrence. The sensitivity and specificity of the assay will be calculated and presented with 90% joint confidence regions. Based upon a cohort size of 110 patients, the joint confidence regions for the sensitivity and specificity will be no wider than  $\pm 0.13$ .

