assay-based response or progression, the proportions of patients with CR/PR, SD, or PD will be presented with exact 90% confidence intervals. We will further characterize the behavior of the assay by comparing assay fold changes with fold changes in tumor burden (post/pre); the relationship will be summarized graphically and using the Spearman rank correlation.

Assay performance data will also be divided into four groups defined by pre-treatment expression and at the first restaging (i.e., +/+, +/-, -/+, -/-) and compared with response. The proportions will be summarized and compared using exact confidence intervals in all four assay combinations and also in the two subgroups with a positive assay at pre-treatment.

The behavior of the blood assay over time will be summarized graphically. The status of the assay (+/-) will be shown at each assessment time for each patient. Graphics will note changes in disease status and times of disease progression and will provide an opportunity examine patient follow-up for patterns of change in the assay.

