### Prognostic Ability of the Assay

Baseline assay results will be categorized as positive or negative and also be described on a continuous scale. The proportion of patients with a positive baseline assay will be presented with a 90% exact binomial confidence interval. Based on a cohort size of 50, the confidence interval will be no wider than 0.25. Confidence intervals will also be presented for the subgroups of patients with intermediate- or high-risk disease. We will also summarize continuous baseline assay levels using descriptive statistics for the complete cohort and according to subgroups.

Preliminary assessments of prognostic ability will be conducted using Kaplan-Meier (K-M) product-limit estimates for relapse or survival and stratified log-rank tests. K-M estimates will be stratified by AJCC stage and assay results to explore assay performance across different prognostic groups. Relapse-free survival and overall survival estimates at pre-specified time points will be presented with 90% confidence intervals estimated using log(-log(survival)) methodology. A secondary analysis will be conducted in the cohort with blood- and tissue-based assessments according to the four groups defined by their combined positive/negative status to look for differences in prognosis.

The relative effect of the blood-based assay with respect to relapse or survival will be estimated using Cox regression models. Since the AJCC staging incorporates prognostic factors such as number of involved nodes, tumor burden, ulceration, and tumor thickness, the Cox models will be stratified by AJCC stage to allow for differences in the baseline hazard of relapse or death. Models will include as covariates age, site of the primary melanoma, sex, and baseline serum LDH in addition to the blood-assay results. We will use aggregated data for the primary models; secondary models will be fit separately for the intermediate- and higher-risk cohorts. Hazard ratios for the assay will be presented with 90% confidence intervals.

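### The planned joint 90% lower bounds, notably about 0.90 for specificity, match a Wald-type region; exact or Wilson limits with 55 patients per class give about 0.79 (sensitivity) and 0.86 (specificity)

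*Combined protocol and SAP*

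**What the plan says.** Section 9.1 (primary objective, advanced cohort) describes the basis of the sizing: "Sample size estimates are based on the binomial distribution and joint 90% confidence regions for sensitivity and specificity". The minimums are set by the statement that the investigators "would require sensitivity of at least 0.80 and specificity of at least 0.90". The planning values follow: "We set our target sensitivity to be 0.90 and specificity to 0.95". With 110 patients, split about 55 and 55 by tissue BRAF status, the plan says that for sensitivity "the lower bound of the joint 90% confidence region will be greater than 0.82" and that "the lower bound of the 90% joint confidence region for the specificity will be approximately 0.90".

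For the exploratory Stage II/resectable Stage III cohort, the same section gives a precision of ±0.13 for the same kind of joint region.

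The text names neither the interval method nor its sidedness. Two references are attached to the sizing sentence, but their content is not part of the documents.

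Elsewhere the plan does name exact intervals for single proportions. Under secondary objective 1, proportions by RECIST category "will be presented with exact 90% confidence intervals". Under Prognostic Ability of the Assay, the proportion with a positive baseline assay gets a "90% exact binomial confidence interval".

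**The concern.** The stated lower bound for specificity equals the minimum the plan requires. A reader would take this to mean that observing the 0.95 target places the joint region at or above that minimum. That depends on how the interval is built. With 55 BRAF-negative patients and specificity 0.95, only 55 × 0.05 = 2.75 false positives are expected, and the Wald interval is known to be too short in that situation. If the figure comes from such an interval, the precision stated for the primary objective is better than n=55 delivers with an interval of adequate coverage. Because no method is named, the same construction could also be carried into the final analysis.

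**Working it through.** **Inputs (all from section 9.1).** n = 55 per class; targets 0.90 (sensitivity) and 0.95 (specificity); joint level 90%; stated bounds above 0.82 and about 0.90; stated ±0.13 in the exploratory cohort. Assumption: the two margins are independent, so each is taken at sqrt(0.90) = 0.9487, giving z = 1.949 two-sided and 1.632 one-sided. A Bonferroni split (95% per margin, z = 1.960) changes the Wald specificity bound only from 0.893 to 0.892.

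**Step 1: reproduce the plan's figures.** Wald lower limit: p − z·sqrt(p(1−p)/n).
- Sensitivity: 0.90 − 1.949·sqrt(0.09/55) = 0.821 (stated: above 0.82).
- Specificity: 0.95 − 1.949·sqrt(0.0475/55) = 0.893 (stated: about 0.90).
- Widest half-width, at p = 0.5 and n = 55: 1.949·sqrt(0.25/55) = 0.131 (stated: ±0.13).

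One form, the two-sided Wald region, therefore accounts for all three. The one-sided Wald form gives 0.834 and 0.902, but its half-width at p = 0.5 is 0.110, which does not fit ±0.13. Wald is not the only form that comes near the two bounds: a two-sided Wald interval on the log scale gives 0.8245 and 0.894, and a one-sided arcsine interval 0.825 and 0.892.

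**Step 2: how that region behaves at the targets.**
- Upper specificity limit: 0.95 + 1.949·sqrt(0.0475/55) = 1.007, above 1.
- Coverage by exact binomial summation. The Wald interval contains 0.90 when 44 to 52 of 55 are positive (probability 0.9153), and contains 0.95 when 48 to 54 of 55 are negative (0.9347). Joint coverage: 0.9153 × 0.9347 = 0.855.
- Same calculation for Wilson: 0.9339 × 0.9440 = 0.882. For Clopper-Pearson: 0.9595 × 0.9807 = 0.941.

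**Step 3: lower bounds with other intervals**, at the targets, n = 55, sqrt(0.90) per margin. Clopper-Pearson uses the non-integer counts 49.5 and 52.25 in the beta quantile.

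| Method | Sensitivity, two-sided | Specificity, two-sided | Specificity, one-sided |
|---|---|---|---|
| Wald | 0.821 | 0.893 | 0.902 |
| Clopper-Pearson | 0.790 | 0.856 | 0.872 |
| Wilson | 0.794 | 0.858 | 0.878 |
| Agresti-Coull | 0.790 | 0.852 | 0.874 |
| Logit | 0.789 | 0.851 | 0.874 |
| Jeffreys | 0.801 | 0.869 | 0.884 |
| Likelihood ratio | 0.804 | 0.872 | 0.887 |
| Arcsine | 0.808 | 0.878 | 0.892 |

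A complementary log-log interval gives 0.785 and 0.847 two-sided, and 0.872 one-sided for specificity. One-sided sensitivity bounds are 0.808 (Clopper-Pearson) and 0.814 (Wilson).

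**Step 4: whole counts.** Two-sided Clopper-Pearson lower limits are 0.849 at 52/55, 0.875 at 53/55 and 0.903 at 54/55. The limit reaches 0.90 only at 54/55 or better (observed 0.982). If true specificity is 0.95, that has probability 0.232. Two-sided Wilson has the same threshold (0.8775 at 53/55, 0.9046 at 54/55).

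**The case against.** **A standard formula gives the plan's figure.** This stands. The number is 0.893 or 0.902 depending on sidedness, and the plan says approximately. A reader might infer an arithmetic error; the documents do not support that. The issue is the choice of interval.

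**Wald is not the only route to the stated bounds.** This also stands. Log-scale Wald and one-sided arcsine come close, so the documents do not prove which formula was used. What can be said is narrower: the two bounds together with ±0.13 match the two-sided Wald form, and no joint limit tried outside the Wald type reaches 0.90 for specificity at the 0.95 target. At 53/55 observed (0.964), some one-sided limits do reach it (Jeffreys 0.904, mid-P 0.901), but that is above the target.

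**No decision depends on the bound.** Correct. The plan does not say that the lower bound must clear 0.80 or 0.90. Read as point estimates, both minimums would be met at the targets with probability 0.993 × 0.944 = 0.937. A reader might infer that the study is likely to fail its own criterion or is undersized; neither follows from the text.

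**The sentence is a planning statement, and nothing says the final region will be Wald.** Also correct. The plan names exact intervals elsewhere, and its Table 1 PPV intervals agree with a logit-scale calculation (first row: 0.742 to 0.908, against the printed 0.74 to 0.91). So under-coverage in the final analysis is a risk left open, not a planned defect. The same facts make the primary planning figure the outlier: a logit-scale specificity bound would be 0.851.

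**Wilson is also below nominal at the targets (88.2%).** True, though closer to 90% than Wald (85.5%). Clopper-Pearson does not have this shortfall.

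**Conclusion.** The concern holds as a matter of interval method and stated precision. At n = 55 per class, the specificity bound of about 0.90 is not delivered by an interval with adequate joint coverage. Two-sided exact or Wilson limits put it at about 0.86, some 0.04 below the stated figure and below the plan's minimum. The sensitivity bound is about 0.79 instead of above 0.82. Across all the methods tried outside the Wald type, the two-sided ranges are 0.79 to 0.81 for sensitivity and 0.85 to 0.88 for specificity. Read one-sided, exact and Wilson limits give about 0.81 and 0.87 to 0.88, still short of 0.90.

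This rests on an even 55/55 split, observed values at the targets, and a joint region built from two margins at sqrt(0.90). The two-sided reading is inferred from ±0.13, not stated. The computed values are firm; the identification of the plan's formula is a close match only. No planned decision is shown to change. Severity: minor to should-fix.

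**What to change.** In section 9.1:
1. Specify a two-sided joint 90% region, consistent with the ±0.13, with Clopper-Pearson limits at sqrt(0.90) per margin. This matches the exact intervals already named under secondary objective 1 and Prognostic Ability of the Assay. Wilson limits are an acceptable alternative.
2. Restate the expected lower bounds at the targets as about 0.79 for sensitivity and 0.86 for specificity. Both choices give these values to two decimals.
3. Keep n = 110.

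A sentence saying whether the 0.80 and 0.90 minimums refer to point estimates or to lower bounds would also help the reader, but the point does not depend on it.

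Cost: a wording change and less favourable stated figures, with no extra patients. Clopper-Pearson is mildly conservative (joint coverage 94.1% at the targets); Wilson is slightly below nominal there (88.2%).

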2. To explore the prognostic and predictive ability of peripheral blood BRAFV600 mutation detection in the cohort of patients with Stage II or resected Stage III disease, we will test isolated PBL and serum from samples obtained from patients following complete resection of their disease but prior to receiving adjuvant therapy or embarking on expectant monitoring. To control for potential variations in circulating BRAF levels at various post-operative time points, patients must have their blood draw at least 4 weeks but no more than 8 weeks following their last surgery. Additionally, all patients with a thick primary melanoma (defined by AJCC as Breslow depth greater than 4 mm) or a clinically apparent/macroscopic involved lymph node, satellite lesion, or in-transit lesion will have tissue-based BRAF analysis performed either at the MGH TRL, at Clariant Laboratories using the FDA-approved Cobas® test, or in MGH pathology using BRAFV600 stain. PBL and serum will be isolated from blood collected in two 10 mL green top tubes on each patient and will then be placed in Trizol Reagent prior to RNA isolation. RNA will then be isolated from tissue and PBL/serum and BRAFV600 analysis will be performed as described above.

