## **2.3 Rationale**

Strategies are underway to improve the effectiveness of BRAF-directed therapy and immune-based therapy, and similar efforts are needed to develop biomarkers with which we may better select treatment for melanoma patients and follow patients while they are being treated. With BRAF-targeted therapy now established as a standard therapy for metastatic melanoma, the development of highly-sensitive, blood-based assays have the potential to greatly improve the care of patients with BRAF-mutant melanoma in four major ways.

First, less than half of all patients with cutaneous melanoma have a tumor that harbors an oncogenic BRAF mutation.(5) In practice, current BRAF mutational analytic techniques are only capable of testing archival tissue and have limited sensitivity. Additionally, test results typically take two to three weeks, when factoring tissue acquisition and shipping issues, which delays the initiation of therapy for typically ill patients. Lastly, very often a patient who previously was diagnosed with an early stage melanoma who recurs will have a fine needle aspiration performed to confirm the diagnosis, and performing BRAF mutational analysis can be challenging due to the small amount of tissue that is obtained during such procedures. We believe that analyzing blood for the BRAF mutation will prove to be a more efficient method of determining a patient's BRAF status and possibly a more reliable one.

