## **2. To investigate the prognostic and predictive ability of peripheral blood BRAFV600 mutational testing in patients with Stage II or resectable Stage III melanoma.**

The investigation of the prognostic and predictive ability of the assay will be based on the cohort of patients with Stage II and resected Stage III disease. Some of these patients will have a tissue-based BRAF assessment and a pre-treatment blood-based BRAF assay, and some of the patients will have the blood-based assay only.

We would expect that 50% of the cohort would have BRAF-mutated disease and that 90% of those patients will have follow-up data from which to assess the predictive ability of the assay. This results in a sample of size 50. BRAF status will be classified as positive or negative based on the post-resection, blood-based assay, and where applicable, for the tissue-based assessment.

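### The ±0.13 precision bound for the Stage II/III cohort counts all 110 patients as tissue-verified, which the plan's own text does not support

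*Combined protocol and SAP*

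**What the plan says.** Section 1.2 recruits 110 patients to each cohort, takes the tissue result as the reference that classes a patient as mutant or not, and limits Stage II/III tissue testing to those with enough tissue. Section 3.1 admits any Stage II or III patient.

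The paragraph on the Stage II/III cohort in section 9.1 makes three statements that bear on precision:

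- On the reference standard: "only patients in this cohort with T4 disease or macrometastatic lymph nodes will have adequate tissue for assessment".
- On expected performance: "We cannot predict the sensitivity and specificity of the assay in patients with Stage II or resected Stage III disease".
- On precision: "Based upon a cohort size of 110 patients, the joint confidence regions for the sensitivity and specificity will be no wider than" ±0.13, with joint 90% regions.

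Secondary Objective 2 in section 9.1 expects half of this cohort to be BRAF-mutated. It also says that "some of the patients will have the blood-based assay only". No section gives the number or share of Stage II/III patients expected to have a tissue result.

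**The concern.** Sensitivity can be estimated only in patients whose tissue is mutant, and specificity only in those whose tissue is wild-type. A patient with the blood assay alone contributes to neither. A width computed on the recruited 110 is therefore a width for a fully verified cohort, and the same paragraph says the cohort will not be fully verified.

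This is the only precision figure given for sensitivity and specificity in this cohort, and it sits under the primary objective. Section 9.1 also presents the cohort as a possible basis for further studies, so a reader planning those studies could rely on it. The stakes are otherwise modest: the cohort is labelled exploratory, no performance threshold is set for it, and the observed regions will be reported in any case.

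**Working it through.** **Inputs.** Joint 90% region, binomial basis, 110 patients (section 9.1). Prevalence 50% in this cohort (section 9.1, Secondary Objective 2), so 110 × 0.5 = 55 mutant and 55 wild-type if all have tissue. Sensitivity and specificity are not predicted, so an upper limit on width has to use p = 0.5.

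**Formula.** For two independent proportions, a joint level of 0.90 means √0.90 = 0.9487 for each, so z = 1.949.

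- Normal half-width: z·√(p(1−p)/n), which at p = 0.5 is 1.949 × 0.5/√n.
- Wilson half-width at p = 0.5: 1.949 × 0.5/√(n + z²).

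**Reproducing ±0.13.** With n = 55, the normal approximation gives 0.131 and Wilson gives 0.127. Both round to 0.13. The alternatives do not fit: 110 in each denominator gives 0.093, and a marginal 90% normal interval with n = 55 gives 0.111.

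As a check on method, section 9.1 plans the advanced cohort with "approximately 55 with BRAF mutation and 55 without". The same formula at sensitivity 0.90 gives a lower bound of 0.90 − 1.949 × √(0.09/55) = 0.821, which agrees with the plan's statement that it exceeds 0.82. For specificity 0.95 it gives 0.893, against a stated value of about 0.90. So ±0.13 is the 55 + 55 calculation.

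**How many tissue results the bound needs.** To round to 0.13, the worst-case half-width must be below 0.135.

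- Normal: n = 52 gives 0.1351 and n = 53 gives 0.1338, so 2 × 53 = 106 patients.
- Wilson: n = 48 gives 0.1354 and n = 49 gives 0.1341, so 2 × 49 = 98 patients.

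**Worst case with fewer tissue results.** The 75% and 50% shares are assumptions. The split is even and group sizes are rounded down.

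| Share with tissue | n per group | Normal | Wilson |
|---|---|---|---|
| 100% | 55 | 0.131 | 0.127 |
| 75% | 41 | 0.152 | 0.146 |
| 50% | 27 | 0.188 | 0.176 |

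**Dependence on the split.** At 40% prevalence with all 110 verified, the groups are 44 and 66, with normal half-widths of 0.147 and 0.120.

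**The case against.** **The limitation is disclosed, and the cohort is exploratory.** Both are true, and both lower the consequence. But the restriction is not carried into the number, which is tied explicitly to 110 patients.

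**Realised regions may be well inside ±0.13.** This stands. With 22 per group (44 verified, 40% of the cohort) and a true value of 0.90, the normal half-width is 1.949 × √(0.09/22) = 0.125. A reader might therefore infer too much by concluding that the design cannot deliver ±0.13; the documents do not show that, because the verified share is unknown and the width depends on accuracy. They do show that an upper limit is not supported, since the plan declines to predict accuracy and its own figure is the p = 0.5 case.

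**Prevalence.** A reader might treat the 50/50 split as a second error. Section 2.3 says that "less than half of all patients with cutaneous melanoma have a tumor that harbors an oncogenic BRAF mutation", and Table 1 gives "90% confidence intervals over a range of prevalence rates of BRAF mutation" from 0.4 to 0.6. But the first is a background remark on all cutaneous melanoma, and the second is a range for positive predictive value in the discussion of the advanced cohort. Neither contradicts the 50% planned for Stage II/III. The 40% result is a caveat only.

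**Exact intervals.** Clopper-Pearson gives 0.137 at n = 55, so it misses ±0.13 even with every patient verified. That reflects the choice of interval, which the plan does not name, and is not evidence about missing tissue.

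**Conclusion.** The arithmetic behind ±0.13 is sound for 55 + 55 patients; the fault is the denominator. The bound holds only if nearly all of the 110 have a tissue result (about 106 by the normal approximation, 98 by Wilson, with an even split), and the plan says that only a subset will have adequate tissue. It is unsupported as written.

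The size of the shortfall cannot be fixed from the documents. If 75% or 50% are verified, the normal worst case is about ±0.15 or ±0.19. These figures assume p = 0.5, independent proportions and 50% prevalence among the verified patients. The error should be corrected, but it changes no sample size, analysis or decision.

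**What to change.** In section 9.1, replace the ±0.13 sentence with text of this kind:

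> We expect tissue BRAF results in [n] of the 110 Stage II/III patients, about [n1] mutant and [n2] wild-type. With these numbers the worst-case half-width of the joint 90% region, by the [named] method, is ±[x] for sensitivity and ±[y] for specificity. These estimates apply to the tissue-verified subset.

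Compute x from the mutant count and y from the wild-type count. If the verified number cannot be predicted, give the half-width over a range of verified counts.

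When estimating the subset, reconcile section 9.1 with section 1.3, where patients with a thick primary "or a clinically apparent/macroscopic involved lymph node, satellite lesion, or in-transit lesion will have tissue-based BRAF analysis performed". Section 9.1 names only T4 disease and macrometastatic nodes. If the wider description applies, more patients are verified and the shortfall is smaller.

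The cost is text plus an estimate of how many patients will have tissue; no extra patients, samples or tests are needed. The downside is that the quoted precision becomes less favourable and covers a narrower group.
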